2.5. Statistical analysis

Continuous variables were stated as mean and standard deviation, and categorical variables as percentages and frequency distribution. The conformity of the data to normal distribution was tested using the Kolmogorov-Smirnov test. For the comparison of continuous variables between the three groups, ANOVA was used for the data that fit the normal distribution, and the independent sample Kruskal-Wallis test was used for the data that did not fit the normal distribution. Categorical variables were compared using a chi-square test. Friedman test was used to assess the repeated measurements of the same group. A $p<0.05$ was set as a statistically significant alpha error.

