2.3. Follow-up and outcome measures

Functional outcomes were assessed with the patient-rated tennis elbow evaluation questionnaire (PRTEE). This outcome score consisted of 15 items related to three subscales, namely pain (5 questions), specific activities (6 questions), and daily activities (4 questions). The total score ranges between 0-100 points, 0 points designates the best functional outcome, whereas 100 points designates the worst functional outcome [12, 13]. To interpret PRTEE results, a minimum clinically important difference (MCID) value previously described by Poltawski et al. was used [14]. According to his study, a 37% decrease in PRTEE is considered a 'complete recovery' or clinically significant change. PRTEE was assessed before the injection (baseline values), on Day 15, Day 30, and Day 90, in the

same manner by the senior author. The same author performed follow-up and data collection. No patients received more than one injection in this clinical trial.

Hand grip strength (HGS) was measured with a digital hand dynamometer before and after injection in all patients. The senior author performed the measurements according to the American Society of Hand Therapists guidelines [15]. Since HGS varies according to factors such as height, weight, age, and gender, each patient's hand grip strength was calculated as a percentage increase from baseline.

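### A Kolmogorov-Smirnov pre-test of unstated form chooses between ANOVA and Kruskal-Wallis, so the between-arm test can differ between Days 15, 30 and 90

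*Combined protocol and SAP*

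**What the plan says.** Section 2.5 sets a two-stage rule for comparing continuous variables between the three arms. The first stage is a normality check: "The conformity of the data to normal distribution was tested using the Kolmogorov-Smirnov test". If normality is not rejected, the comparison is on means: "ANOVA was used for the data that fit the normal distribution". If it is rejected, the plan turns to a rank test instead: "the independent sample Kruskal-Wallis test was used for the data that did not fit the normal distribution". A p-value below 0.05 "was set as a statistically significant alpha error"; no separate level is given for the pre-test.

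The section does not say:
- whether the Kolmogorov-Smirnov test is uncorrected or in the Lilliefors form, which allows for the estimated mean and SD;
- whether it is applied to each arm, to pooled data or to residuals;
- what happens when the arms disagree;
- whether one test is kept for all visits.

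Section 2.3 supplies the repeated occasions: "PRTEE was assessed before the injection (baseline values), on Day 15, Day 30, and Day 90". Section 2.4 sizes the trial for a three-group ANOVA. For change within an arm, section 2.5 has no normality condition: "Friedman test was used to assess the repeated measurements of the same group".

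**The concern.** The between-arm test is chosen from the outcome data, and nothing prevents a fresh choice at each visit. The introduction's hypothesis joins early relief from corticosteroid with lower recurrence from autologous blood, so it is read by setting early visits beside Day 90. If Day 15 is tested on means and Day 90 on ranks, the two p-values address different hypotheses, and only the first matches the test behind the sample size.

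The open details also leave room for choice after the data are seen. Treatment was unblinded (section 2.2), the senior author injected and assessed (sections 2.2 and 2.3), and the contribution statement gives data acquisition and analysis to the same author.

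**Working it through.** **Inputs from the documents.** Three arms of 40 (sections 2.2 and 2.4), 33 per arm before dropout (2.4), three follow-up visits (2.3), alpha 0.05 (2.5).

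**Assumptions.** Pre-test level 0.05; the form and unit of the pre-test, varied below; Kruskal-Wallis at a visit if any arm rejects, for the per-arm versions; the distribution shapes; visit correlation 0.6. For per-arm Lilliefors at 40 per arm, correlations of 0, 0.5 and 0.7 gave similar results (36% to 37% with normal data, 59% to 62% with gamma(4)).

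**1. The plan's own figure.** The plan gives no figure for the pre-test. Its 33 per arm at 90% power corresponds to f = 0.363 in a three-group ANOVA. This cannot be derived from a 37% change and SD 10 without a baseline mean. For equally spaced means with end-to-end distance d in SD units, f = (d/2)√(2/3), so d = 0.363/0.408 = 0.89; step 5 uses 0.88. Dropout: 99 × 1.2 = 118.8, about 120. The point needs only the fact that ANOVA was assumed.

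**2. Chance of mixed tests, by hand.** Let p be the chance that a visit goes to Kruskal-Wallis. With three independent visits, P(mixed) = 1 − p³ − (1 − p)³ = 3p(1 − p).
- Lilliefors per arm, normal data: p = 1 − 0.95³ = 0.143; 3 × 0.143 × 0.857 = 37%.
- One pooled Lilliefors test per visit, normal data: p = 0.05; 3 × 0.05 × 0.95 = 14%.
- Uncorrected, per arm, normal data: simulated true size 0.00008 per arm at n = 40, so p ≈ 0.00024 and P(mixed) ≈ 0.07%.
- Lilliefors per arm, gamma(4) (skewness 1): simulated p = 0.706; 3 × 0.706 × 0.294 = 62%.
- Uncorrected, per arm, gamma(4): simulated p = 0.031; 3 × 0.031 × 0.969 = 9%.

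**3. The same by simulation**, 40 per arm, visit correlation 0.6. Share of trials mixing tests over the three follow-up visits:

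| Shape (same at every visit) | Lilliefors, per arm | Lilliefors, pooled residuals | Uncorrected, per arm |
|---|---|---|---|
| Normal | 36%–38% | about 15% | about 0.1% |
| Gamma(4), skewness 1 | 59%–62% | about 50% | 8%–10% |
| Gamma(2) | 19% | not tabulated | 33% |
| Exponential, skewness 2 | about 0.2% | not tabulated | about 68% |

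Mixing peaks where p is near one half. Lilliefors reaches that region at mild skew and the uncorrected form at strong skew.

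**4. Type I error**, over eight shapes at 33 and 40 per arm:
- fixed ANOVA 4.5%–5.3%;
- fixed Kruskal-Wallis 4.5%–5.2%;
- two-stage with Lilliefors 4.6%–5.4%;
- two-stage with uncorrected Kolmogorov-Smirnov 4.7%–5.7%.

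Reporting whichever test is significant gives 5.8%–6.9% per comparison at 40 per arm (exponential, lognormal, t with 3 degrees of freedom, and two normals floored at zero). This is what free choice between the two tests could add.

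**5. Does the choice change the answer?** For shifts of 0.5 to 0.88 SD, ANOVA and Kruskal-Wallis disagree on significance in 2%–11% of trials at skewness 0 to 1, and in 6%–33% at skewness 2.

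**The case against.** The strongest reply is that error rates are hardly touched and the rule can help. Lilliefors holds 5% per test and flags exponential data at over 99% of visits, and the two-stage rule then follows the more powerful test. At skewness 1 and 33 per arm, with means 0.88 SD apart, power is 91.9% for two-stage Lilliefors against 88.8% for fixed ANOVA. With an exponential shape, a 0.5 SD shift and 40 per arm, it is 83.1% for Kruskal-Wallis against 50.4% for ANOVA. On PRTEE, "The total score ranges between 0-100 points, 0 points designates the best functional outcome", so skew after recovery is plausible. This stands. It argues for a rank analysis named in advance at every visit, not for letting each visit's data choose.

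Four stronger readings are tempting, and the documents do not support them:
- **The pre-test inflates false positives.** It does not; see step 4.
- **The pre-test fails in both usual forms, and the faults add up.** Near-inertness (about 1% rejection per arm at skewness 1) belongs to the uncorrected form. Chance switching with normal or mildly skewed data belongs mainly to Lilliefors. The trial uses one form, and the plan does not say which.
- **Early and late results could not be read on one scale.** Section 2.5 summarises continuous variables by mean and SD with no normality condition, so PRTEE means appear at every visit. What is missing is a consistent test and a confidence interval for the difference.
- **The analyst used the freedom.** The documents show opportunity only.

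The lack of baseline adjustment would apply equally to plain ANOVA, so the pre-test does not cause it.

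**Conclusion.** The concern holds in a limited form. Section 2.5 lets an incompletely specified normality test on the outcome data choose the between-arm test, and nothing keeps that choice constant across Days 15, 30 and 90. The chance of mixed tests runs from about 0.1% to 38% with normal data and from 8% to 62% at skewness 1. With exponential data it is almost nil for per-arm Lilliefors and about 68% for the uncorrected form. No single figure can be assigned to this trial, because the form, the unit, the switching rule, the shapes and the visit correlation are all assumed.

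Type I error remains near 5%, so the results would not be invalid. The cost is to consistency of the hypothesis, to pre-specification, and to precision from the baseline PRTEE that section 2.5 leaves unused. The pre-test is not needed for validity at this size. The change should be made, though the trial's validity does not depend on it.

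**What to change.** In section 2.5, remove the normality test as a decision rule. For PRTEE at every follow-up visit, name one linear model with arm and baseline PRTEE, and report adjusted arm differences in PRTEE points with 95% confidence intervals. Run Kruskal-Wallis at every visit as a fixed sensitivity analysis, whatever the distribution looks like. Robust standard errors are optional; nothing here shows that they are needed.

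The chance of switching then falls to zero, and the main analysis stays in the ANOVA family used for the sample size. Baseline adjustment also adds precision: if the assumed correlation of 0.6 held between baseline and follow-up, residual variance would fall to 1 − 0.6² = 0.64 of its unadjusted value. The cost is one sentence and no new data, since baseline PRTEE is already collected. If the analysis has already been run, state which form and unit of the pre-test were used and which test was applied at each visit, and label the fixed model as added afterwards.

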Lateral epicondylitis (LE) is a common musculoskeletal disorder affecting the extensor tendons of the forearm, manifesting as pain on the lateral side of the elbow and functional limitation during daily activities. Despite its name suggesting inflammation, histopathological examinations of the tendon reveal non-inflammatory angiofibroblastic tendinosis, accompanied by neovascularization, disorganized collagen, and mucoid degeneration [1, 2]. Since tendon degeneration is the underlying pathology, an effective therapeutic approach should reverse the degeneration to regeneration, ensuring symptom relief without recurrence.

Although many treatments exist, a consensus on the optimal single treatment for LE remains elusive. Traditionally, injections have served as a preliminary measure before resorting to surgical interventions, especially in resistant cases. However, an increasing number of alternative injections have been described in recent literature [3]. Newer injection therapies, such as autologous blood (AB) injections and platelet-rich plasma (PRP), have gained prominence and found favor among orthopedic surgeons. Multiple studies have attested to the safety and efficacy of AB and PRP injections as treatment modalities [4-7]. However, corticosteroid (CS) injections continue to be among the most commonly employed treatments for LE. A significant drawback of CS injections is their high recurrence rate. Patients typically experience a swift recovery immediately after injection, which endures for about a month. Unfortunately, this transient relief—often referred to as the 'honeymoon period'—is short-lived, leading to a recurrence of symptoms. Such a response pattern is well-documented in existing studies [8]. Conversely, AB injection therapy tends to proffer a gradual yet consistent reduction in symptoms, boasting a recurrence rate markedly lower than that of CS. It is postulated that AB addresses the intrinsic degeneration of the tendon, with its restorative process inherently spanning a more extended period [9-11].

We hypothesized that a combination of CS and AB injection might offer a superior treatment for LE. This combination may provide a faster resolution of symptoms due to the initial action of CS and provide a lower recurrence rate due to the regenerative action of AB. The purpose of this randomized clinical trial is to test three different types of injection for the treatment of LE: (1) AB, (2) CS, and (3) their combination (AB+CS).

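### The planned tests never compare the combination with AB or with CS, so they cannot by themselves support the hypothesis that the combination is superior

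*Combined protocol and SAP*

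**What the plan says.** The Introduction states the hypothesis: "We hypothesized that a combination of CS and AB injection might offer a superior treatment for LE". It gives two mechanisms: "This combination may provide a faster resolution of symptoms due to the initial action of CS", and that it would "provide a lower recurrence rate due to the regenerative action of AB". It also gives a neutral aim: "The purpose of this randomized clinical trial is to test three different types of injection for the treatment of LE". The background describes the time course expected of each single treatment. For CS, "Patients typically experience a swift recovery immediately after injection, which endures for about a month", after which symptoms return. By contrast, "AB injection therapy tends to proffer a gradual yet consistent reduction in symptoms".

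Section 2.5 covers between-group comparison in one rule: "For the comparison of continuous variables between the three groups, ANOVA was used for the data that fit the normal distribution", Kruskal-Wallis otherwise, and chi-square for categorical data. The Friedman test is for repeated measurements inside one group. The threshold is p<0.05.

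Section 2.3 schedules PRTEE at baseline and Days 15, 30 and 90 without ranking the visits. It also adopts a responder threshold, in the sentence containing "a 37% decrease in PRTEE is considered a". Section 2.4 sizes the trial on PRTEE with a three-group ANOVA. No section names a pairwise comparison, a primary visit or an adjustment for multiple tests.

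**The concern.** The hypothesis is about one arm and has a direction. The natural comparators are AB for speed and CS for durability; this is an inference, since the text does not name them. None of the listed tests makes either comparison. A three-group test asks only whether the arms are all equal. It can be significant because the combination is best, because it is worst, or because it matches CS and only AB differs. The Friedman test compares visits within one arm and says nothing about another arm. Chi-square on the 37% threshold would again compare three groups, with no visit named and no definition of losing a response.

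The trial could therefore report p<0.05 at some visit without having tested its hypothesis. The pair, visit and adjustment would then be chosen after the results are known. That matters more here because one unblinded author injects, follows up and collects the data (Sections 2.2 and 2.3).

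**Working it through.** **1. The plan's own figure.** Section 2.4 gives a 37% change from baseline PRTEE, SD 10, alpha 0.05, power 0.90, three-group ANOVA and 33 per group. The 33 cannot be reproduced, because no baseline mean and no pattern of group means is given. It can be inverted. With one arm differing by d SDs, the noncentrality is n × (2/3) × d². For n = 33 and power 0.90, d = 0.770: 33 × (2/3) × 0.770² = 13.0, which gives power 0.90 on 2 and 96 degrees of freedom. At SD 10 this is 7.7 points. With evenly spaced means, the extremes must be 8.9 points apart. For comparison, 37% of an assumed baseline of 20, 30 or 40 is 7.4, 11.1 or 14.8 points. The 7.7 used below is therefore an assumption near the low end.

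**2. Hypothesis against tests.**

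| Part of hypothesis | Comparison needed | Planned test |
|---|---|---|
| Faster resolution | Combination v AB, early | None; three-group test only |
| Lower recurrence | Combination v CS, late | None; three-group test only |
| Change within an arm | Not a comparison of arms | Friedman |

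**3. Can the three-group test tell success from failure?** Two scenarios follow the Introduction's time courses.

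- A (hypothesis true): early, combination = CS and AB is worse by 7.7; at Day 90, combination = AB and CS is worse by 7.7.
- B (AB adds nothing): combination = CS throughout; AB is worse by 7.7 early and better by 7.7 at Day 90.

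At each visit exactly one arm differs by the same amount, so the noncentrality, and hence the power, is identical in A and B at any effect size. Simulated results (SD 10, complete data, unadjusted t-tests for the contrasts):

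| | A | B |
|---|---|---|
| Three-group test significant at both visits, 33 per group | about 80% | about 80% |
| Same, 40 per group | about 90% | about 90% |
| Combination beats AB early and CS at Day 90, 33 per group | 76-77% | 2.3-2.6% |

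The two contrasts separate A from B; the three-group tests do not. The 80% and 90% are illustrations that depend on the 7.7 points. The equality per visit does not.

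**4. False positives if any visit may be claimed.** With no true effect and independent visits, 1 − 0.95³ = 14.3%. The documents give no visit correlation, so it is varied (33 per group, simulated):

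| Assumed correlation | 0.3 | 0.5 | 0.7 | 0.8 | 0.9 |
|---|---|---|---|---|---|
| At least one p<0.05 | 14% | 13% | 11% | 10% | 8.5% |

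Tests of grip strength would add to this, but Section 2.3 does not say how often it was measured after injection.

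**5. What the two contrasts can and cannot show.** Each must be significant at two-sided 0.05 in one direction, so if either true difference is zero the chance of passing is at most 0.025. But suppose the combination is the middle arm at both visits: AB 7.7 worse and CS 7.7 better early, then CS 7.7 worse and AB 7.7 better at Day 90. It passes in about 76-78% of trials at 33 per group, much as when the hypothesis is true.

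**6. Joint power of the two contrasts** (33 per group, SD 10, visit correlation 0.5, unadjusted, combination ahead in both by the stated amount):

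| Points | 7.4 | 7.7 | 8.9 | 11.1 | 14.8 |
|---|---|---|---|---|---|
| Joint power | 0.72 | 0.77 | 0.90 | 0.99 | 1.00 |

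At 7.7 points it is 0.86-0.87 with 40 per group, and 0.74-0.76 with the 40 × 0.8 = 32 left after 20% dropout. If SD 10 is the unadjusted SD and PRTEE correlates 0.5 with baseline, the residual SD is 10 × √(1 − 0.25) = 8.66. Then 7.7 points acts like 7.7/0.866 = 8.9, for a joint power of about 0.90 at 33 per group.

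**The case against.** The best defence is that the Introduction also states a neutral aim, which a three-group test serves, and that the hypothesis is worded cautiously. Group means would show direction, and PRTEE is in effect the main outcome because the trial is sized on it. All of this stands. It means that the three-group test is not invalid and that the real outcome gap is the visit. It does not supply a test of the hypothesis: means without a contrast or interval are descriptive, and no follow-up tests are written down.

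Second, the 8-14% depends on an any-visit rule that no section states. That is correct. A reader might infer that the trial's error rate is 14%. The documents do not support this; they only fail to exclude such a use.

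Third, a reader might infer that winning both contrasts would prove overall superiority or lower recurrence. It would not. A middle-ranking combination passes, and mean PRTEE at Day 90 does not measure recurrence.

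Fourth, 7.7 points is back-solved from the sample size, so a single figure for lost power would mislead. This stands, which is why a range is given. Finally, the two-contrast model is one design among several, and Sections 2.2 to 2.5 are in the past tense. If outcomes have been seen, no contrast chosen now can confirm the hypothesis.

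**Conclusion.** The concern holds in a limited form. As written, the analysis contains no test of the combination against either single treatment, and so cannot by itself support the stated hypothesis. That conclusion rests on the text alone. That three-group tests respond equally to success and to a combination no different from CS holds at each visit for any effect size, given the Introduction's time courses and equal-sized differences. The false-positive figure of about 8-14% is conditional on an any-visit claim and on assumed visit correlations of 0.9 to 0.3. The power figures are conditional on the assumed difference, SD 10 and complete data. The documents do not support saying that the three-group tests are wrong for the neutral aim, or that the trial will be over-interpreted. They leave that open.

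**What to change.** Name PRTEE as primary, with two contrasts: combination versus AB at one early visit fixed in advance (Day 15 or Day 30), and combination versus CS at Day 90. Estimate both from one model with baseline PRTEE, group, visit and group-by-visit. Add a rank-based sensitivity analysis to keep Section 2.5's provision for non-normal data.

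- If both are significant at two-sided 0.05 in the combination's favour, claim only that it was better than AB early and better than CS at Day 90. Use Holm if either alone may be claimed.
- Report combination versus CS at the early visit and versus AB at Day 90 beside them, with confidence intervals. Make no wider claim unless these show that the combination is not worse.
- As the secondary measure closest to recurrence, report the proportion with at least a 37% PRTEE reduction at Day 30 that is still met at Day 90.
- Treat the three-group tests, other visits and grip strength as secondary.
- Restate power for the two contrasts over a range of differences.

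The cost is analysis-plan wording and two model contrasts, with no new data. Other visits could no longer be headlined. At 33 per group without baseline adjustment, joint power falls below 0.90 only if the true difference is under about 9 points. If outcome data have already been examined, the contrasts must be labelled exploratory and cannot confirm the hypothesis.

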2.4. Sample size calculation

In our pursuit to determine the optimal sample size for our study on LE treatments utilizing PRTEE scores, we based our assumptions on several crucial parameters. We anticipated a 37% change in baseline PRTEE scores and considered a standard deviation (SD) of 10, drawing from previous studies. We adopted a conventional significance level (α) of 0.05 and aspired for a power of 0.90, applying the ANOVA testing methodology for three distinct treatment groups. Our computations indicated that to discern this 37% shift in PRTEE scores with the targeted power and significance level, a sample size of roughly 33 participants per group would be essential. Thus, given the three treatment groups in our research design, the aggregate sample size was estimated at 99 participants. However, taking into account a 20% dropout rate, the study included a total of 120 patients, with 40 patients in each group.

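### Section 2.5 plans no pairwise between-arm estimate with a confidence interval, no between-arm comparison over time and no baseline adjustment of PRTEE, although baseline PRTEE is collected

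*Combined protocol and SAP*

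**What the plan says.** Section 2.5 is the whole analysis plan. For differences between arms it says: "For the comparison of continuous variables between the three groups, ANOVA was used for the data that fit the normal distribution"; data that fail the normality check go to Kruskal-Wallis, and categorical variables to chi-square. For repeated measurements it says: "Friedman test was used to assess the repeated measurements of the same group". For summaries: "Continuous variables were stated as mean and standard deviation". Significance is p<0.05. No covariate, pairwise comparison, treatment-by-visit comparison or confidence interval is named.

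Section 2.3 shows what data exist: "PRTEE was assessed before the injection (baseline values), on Day 15, Day 30, and Day 90". Grip strength is measured before and after injection, at follow-up times that are not named, and "hand grip strength was calculated as a percentage increase from baseline". Whether PRTEE is to be analysed as the raw score, the change or the percent change is not stated.

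The hypothesis is in the Introduction: "This combination may provide a faster resolution of symptoms due to the initial action of CS and provide a lower recurrence rate", the latter credited to autologous blood (AB). Section 2.4 "considered a standard deviation (SD) of 10, drawing from previous studies", without saying whether this is the SD of the score or of the change.

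**The concern.** The case for the combined injection has two parts: quicker relief than AB, and better durability than corticosteroid (CS). These are two named pairwise contrasts, one early and one late. A three-arm omnibus p-value at a visit does not say which arm differs, in which direction or by how much. Friedman shows whether scores move within an arm and cannot compare arms. As planned, the trial could report significance without estimating either contrast, and nothing addresses whether a difference between arms shifts from Day 15 to Day 90.

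Baseline PRTEE is also measured in every patient and then given no role in the between-arm comparison, unless a change or percent-change score is meant. Using it as a covariate usually makes the estimates more precise at very little cost.

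**Working it through.** **Inputs from the documents.** SD 10, alpha 0.05, power 0.90 and 33 evaluable per arm (section 2.4, where "the study included a total of 120 patients, with 40 patients in each group" after allowing for dropout); PRTEE at baseline and Days 15, 30 and 90 (section 2.3).

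**Assumptions (not in the documents).** Baseline-to-follow-up correlation ρ = 0 / 0.3 / 0.5 / 0.7; ratio k of follow-up SD to baseline SD; correlation r between visits.

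**1. The plan's own figure.** The 33 per arm cannot be derived from the stated inputs, because a 37% change needs a baseline mean and a pattern of arm means. Reading 37% as Cohen's f = 0.37 gives 32 per arm (power 0.902; 0.911 at 33), but then SD 10 is not used. Working back from 33 per arm and 0.90 power by noncentral F gives f = 0.363. With one arm differing, f = Δ√2/(3 × 10), so Δ = 0.363 × 30/√2 = 7.70 points. This is a back-solved reference value, not a figure in the plan. Interval widths do not depend on it.

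**2. Against raw-score ANOVA, if SD 10 is the SD of the score.**
- Unadjusted half-width: t(96) × 10 × √(2/33) = 1.985 × 2.462 = 4.89 points.
- Adjusted: multiply by √(1 − ρ²), with 95 df.

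| ρ | variance cut | half-width | power at 7.70 points |
|---|---|---|---|
| 0 | 0% | 4.89 | 0.8999 |
| 0.3 | 9% | 4.66 | 0.926 |
| 0.5 | 25% | 4.23 | 0.965 |
| 0.7 | 49% | 3.49 | 0.996 |

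Unadjusted power is 0.9000. If 37% is instead a between-arm difference at an assumed baseline mean of 50 (0.37 × 50 = 18.5 points), unadjusted power already exceeds 0.999 and only interval width is at stake.

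**3. Against change scores.** The ratio of ANCOVA to change-score variance is k²(1 − ρ²)/(1 + k² − 2ρk), which becomes (1 + ρ)/2 when k = 1.

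| k | variance cut at ρ = 0 / 0.3 / 0.5 / 0.7 |
|---|---|
| 1 | 50 / 35 / 25 / 15% |
| 1.5 | 31 / 13 / 4 / 0.2% |
| 0.63 | 72 / 65 / 61 / 61% |

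Example, k = 1.5 and ρ = 0.5: 2.25 × 0.75/(1 + 2.25 − 1.5) = 1.6875/1.75 = 0.964, a cut of 4%. The 50 / 35 / 25 / 15% row holds only if the two SDs are equal.

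**4. Against percent change.** Simulation with 20,000 replicates, normal data, SD 10 at both times, assumed baseline mean 50 and a 7.70-point difference: percent-change power 0.75 / 0.88 / 0.955 / 0.993, ANCOVA 0.90 / 0.92 / 0.965 / 0.996. The gain is 0.15 / 0.04 / 0.01 / 0.003, small from ρ = 0.5 upward under these assumptions.

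**5. Between-arm difference in Day 15-to-Day 90 change.** Half-width t(96) × 10 × √(2(1 − r) × 2/33) = 5.78 / 4.89 / 3.79 points at r = 0.3 / 0.5 / 0.7. The data can support such an estimate; the plan reports none.

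**The case against.** The strongest reply is that nothing planned is wrong. Unadjusted ANOVA and Kruskal-Wallis are valid under randomisation, the natural reading is that arms are compared at each visit, and the precision gain is unknown and may be nil. The planned means and SDs, with arm sizes, let a reader calculate unadjusted pairwise intervals. Chi-square would allow the arms to be compared on the 37% response. Faster resolution and lower recurrence can be addressed by an early and a late by-visit comparison, without a change-over-time contrast.

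Much of this stands. A reader might infer that the analysis is biased, or that the arms are never compared at individual visits; the documents support neither. A reader might also take the Day 15-to-Day 90 contrast as a test of recurrence. It is not: recurrence is an event within a patient, and this contrast compares mean trajectories, so it can only be supportive.

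Nor do the documents support calling percent increase in grip strength a clear error. Section 2.3 gives a reason for it, and the follow-up visits are not named. In simulations over 16 scenarios (assumed mean 25 kg, coefficient of variation 0.4), raw ANCOVA ran from 0.02 below to 0.23 above the better percent-change test in power, and log-scale ANCOVA from 0.04 below to 0.19 above.

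What the reply does not remove is that the two contrasts in the hypothesis are not planned as estimates. Intervals worked out by a reader are unadjusted, and published means and SDs by visit do not yield the contrast over time.

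**Conclusion.** The point holds as a gap in estimation and an avoidable loss of precision, worth correcting but not a threat to validity. The missing pairwise estimates, intervals and between-arm comparison over time follow from the text alone and need no assumption.

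The gain from baseline adjustment is conditional on the correlation, the SD ratio and the PRTEE variable analysed, none of which the documents give. Against raw scores it runs from nothing at correlation 0 to a half-width of 3.49 instead of 4.89 points at 0.7. Against change scores the variance cut runs from 0.2% to 72% over the SD ratios considered. The power figures also assume normal data and the back-solved 7.70 points. It would be too strong to conclude that adjustment always narrows the intervals or that the trial is underpowered without it.

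**What to change.** In section 2.5:

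1. Analyse follow-up PRTEE with a mixed model containing treatment, visit, treatment-by-visit, baseline PRTEE and baseline-by-visit, in place of the unadjusted ANOVA/Kruskal-Wallis for PRTEE. Keep the rank test as a sensitivity analysis. Separate ANCOVAs by visit would not themselves give the interval for change over time.
2. Report combined v AB and combined v CS differences with 95% CIs at Days 15, 30 and 90. Name in advance, as lead comparisons, combined v AB at the early visit (saying which visit that is) and combined v CS at Day 90. Otherwise six by-visit intervals and two change contrasts stand with no order of importance. Report the between-arm difference in Day 15-to-Day 90 change as supportive.
3. Treat within-arm Friedman results as descriptive.
4. The text is in the past tense. If outcomes have been seen, label the adjusted analysis post hoc and report the planned tests beside it.

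Baseline-adjusted grip strength is optional, as a sensitivity analysis only.

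Cost: new wording, slightly more analysis work and no new data. In a by-visit ANCOVA the baseline term takes one degree of freedom, moving power from 0.9000 to 0.8999 at zero correlation.
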